#### **Other Objectives:**

Other exploratory objectives include:

- 1. Assessing visual acuity with the study lenses;
- 2. Assessing lens fit characteristics;
- 3. Assessing lens wear time compliance;
- 4. Assessing subject's responses regarding lens vision, comfort and handling performances.

In addition, the performance of the three Test lenses (EMO-114, -116, and -118) for myopia control may be evaluated and compared with the Control lens (EMO-117) for one year of lens wear, if applicable. Summary statistical analyses will be performed on safety and efficacy parameters of available 1-year data.

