#### Secondary Hypothesis:

Secondary endpoint and all other safety endpoints will be summarized descriptively. No secondary endpoint hypothesis testing will be performed.

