#### **14. STATISTICAL METHODS**

#### 14.1. General Considerations

Statistical Analysis will be undertaken by the Sponsor. A general description of the statistical methods to be implemented in this clinical trial is outlined below.

All data summaries and statistical analyses will be performed using the SAS software Version 9.4 (SAS Institute, Cary, NC). Throughout the analysis of data, the results for each subject/eye will be used when available for summarization and statistical analysis. Unscheduled visits will be summarized separately and will be excluded from the statistical analysis.

Summary tables (descriptive statistics and/or frequency tables) will be provided for all baseline variables, efficacy variables and safety variables as appropriate. Continuous variables will be summarized with descriptive statistics (n, mean, standard deviation (SD), median, minimum and maximum). Frequency count and percentage of subjects or eyes within each category will be provided for categorical data.

All statistical analysis will be conducted on the per-protocol population defined in section 14.3.

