#### 14.7. Other Analyses

If the primary objective of the study is met, additional analysis may be performed to compare among three Test lenses, including comparisons between Test 1 and Test 2 vs. Test 3 lenses.

In addition, the performance of the three Test lenses (EMO-114, -116, and -118) for myopia control may be evaluated and compared with the Control lens (EMO-117) after 1-year of lens wear, if data are available.

Summary statistical analysis will be provided for the following other observations for the entire study, including 1-year data, if available:

- 1. Non-significant AEs and non-ocular AEs
- 2. Slit lamp findings per the ISO 11980 grading scale
- 3. Subject-reported ocular symptoms
- 4. Corneal radius of curvature measured by an autorefractor

- 5. Over-the-lens near visual acuity
- 6. Subjective best-sphere over-refraction
- 7. Number of power modification per each prescription update
- 8. Number of prescription update during the study
- 9. Lens fit characteristics
- 10. Distance logMAR visual acuity under High Luminance High Contrast (HLHC) conditions
- 11. Subjective vision, comfort, and handling scores based on the Pediatric Contact Lens User Experience (pCLUE) questionnaire.
- 12. Lens wear time compliance, including weighted average of daily lens wear time (in hours), average number of lens wear days per week, and a composite lens wear time compliance score (%) relative to protocol specified minimum and recommended lens wear time requirements, per each dispensing period and for the entire study
- 13. Number of visits for contact lens insertion/removal training
- 14. Subject's demographics
- 15. Subject's disposition, number and reasons for discontinuation
- 16. Number and reasons for unscheduled visits
- 17. Lens accountability, including reasons for lens dispensing or replacement
- 18. Protocol deviations
- 19. Product quality complaints

Further exploratory analysis will be considered at discretion of the Study Responsible Clinician.

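### Section 14.1 puts all statistical analysis on per-protocol Visit 6 completers and no analysis uses the Safety Population: read literally, the 14.7 safety tables omit early withdrawals, and on any reading the safety denominators are unnamed

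*Combined protocol and SAP*

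**What the plan says.** Section 14.1 sets the general rule: "All statistical analysis will be conducted on the per-protocol population defined in section 14.3". Section 14.3 defines three sets:

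- The per-protocol set requires completion of Visits 1, 2 and 6 and no substantial deviation.
- The Safety Population is everyone given a test article, with at least one observation.
- The ITT set is everyone randomized, with at least one observation.

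No analysis section refers to the last two.

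Section 14.6 summarizes serious and significant ocular adverse events from all data available over the whole study, unscheduled visits included. It names no population or denominator.

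Section 14.7 opens with "Summary statistical analysis will be provided for the following other observations for the entire study, including 1-year data, if available". Its list includes "Non-significant AEs and non-ocular AEs", slit lamp findings, ocular symptoms, "Subject's disposition, number and reasons for discontinuation" and protocol deviations. It names no population and does not mention data from unscheduled visits. Section 2.1 (Other Objectives) uses the same label for safety: "Summary statistical analyses will be performed on safety and efficacy parameters of available 1-year data".

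Other text points to a narrower rule. Section 14.1 also says "All data summaries and statistical analyses will be performed using the SAS software Version 9.4" and "Unscheduled visits will be summarized separately and will be excluded from the statistical analysis", and section 2.3 says "Secondary endpoint and all other safety endpoints will be summarized descriptively". Section 14.1 asks for counts and percentages of subjects or eyes for categorical data.

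**The concern.** Safety is the secondary objective (section 2.1), judged on adverse events, slit lamp findings and symptoms in children aged 7 to 12. Leaving before Visit 6 can be a consequence of a safety event. Section 8.2 withdraws a child after a corneal infiltrative event, and section 13.1 classes the non-significant infiltrative event among the non-significant adverse events, which are tabulated only under 14.7. A child withdrawn for such an event before Visit 6 cannot be in the per-protocol set. Non-ocular events, serious ones included, also appear only under 14.7, because 14.6 is confined to ocular events.

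If the 14.1 sentence governs those tables, they lose the events of children who left early. If it does not, nothing says which children each percentage refers to, and that choice is left until after the data exist. Section 14.2 says the data will inform later trials, so an ill-defined adverse event rate would carry forward.

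**Working it through.** The plan gives no figure to reproduce here. The check is textual, with arithmetic to show direction and range.

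**Does the literal rule reach the safety tables?** The 14.1 sentence covers statistical analysis without exception. Section 14.7 and section 2.1 apply that term to the safety outputs. The reference in 14.7 to the whole study fixes a time span, not a population. Section 14.6 is purely descriptive, yet it expressly brings in all available data and unscheduled visits. Section 14.7 has no such override. The literal reading is therefore available.

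**Can the rule work for the rest of the same list?** No. Disposition, reasons for discontinuation and deviations cannot usefully be reported on completers without substantial deviations. The sentence is too broad for the plan's own outputs.

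**Share of exposed children left out.** Section 4.3 gives about 240 enrolled and at least 160 completing. Section 6.1 allows up to 60 completers per lens.

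- At the 4.3 target: (240 − 160)/240 = 33%. Enrollment is counted at consent, so the 240 includes screen failures and this overstates the share.
- At the 6.1 maximum: 4 × 60 = 240 completers, and (240 − 240)/240 = 0%.

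**Direction of the error.** Let N be the number exposed, C the completers, E the affected children, and w the share of affected children who leave before Visit 6. Treat completers as the per-protocol set, although 14.3 also removes substantial deviators.

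- Safety Population rate = E/N
- Completer-only rate = E(1 − w)/C
- The two are equal when w = 1 − C/N

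With C = 160 and an assumed 5% event rate (N and the rate are not in the documents):

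| N exposed | E | Safety rate | w = 0 | w = 1 − C/N | w = 0.5 | w = 1 |
|---|---|---|---|---|---|---|
| 200 | 10 | 5.0% | 10/160 = 6.3% | w = 0.20: 8/160 = 5.0% | 5/160 = 3.1% | 0/160 |
| 240 | 12 | 5.0% | 12/160 = 7.5% | w = 0.33: 8/160 = 5.0% | 6/160 = 3.8% | 0/160 |

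The completer-only count falls short whenever w > 0. The rate is too high if few affected children leave early and too low if many do. For example, with 5% affected among 160 completers and 15% among 40 non-completers (both assumed), the events are 8 + 6 = 14. The table then shows 8/160 = 5.0% against 14/200 = 7.0%.

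**Denominator for 14.6.** The count does not depend on the reading, but the percentage does. Four events (assumed) give 4/160 = 2.5%, 4/200 = 2.0% or 4/240 = 1.7%, a ratio of up to 240/160 = 1.5.

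**The case against.** The strongest reply is that the 14.1 sentence was never meant for safety. Section 14.1 repeatedly separates summaries from statistical analysis, and it says each child's results are used when available for both. Section 2.3 makes safety descriptive, with no testing of the secondary endpoint. The disposition items in 14.7 suggest that the sponsor did not intend a completer-only list. On this view the 14.7 label is loose wording, and the purpose of the Safety Population is clear from its name.

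The events most likely to end participation are also largely covered elsewhere. Significant and serious ocular events, which include significant infiltrative events and microbial keratitis, fall under 14.6. Section 13.1 describes non-significant events as usually not warranting discontinuation. Section 13.5.1 sends symptomatic infiltrates to the DMC.

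Much of this stands. The loss of events is conditional on the literal reading, and the documents do not settle which reading was intended. But the softer reading only moves the gap: it leaves every safety percentage without a named population.

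Some stronger inferences should be resisted:

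- **That serious ocular events would be lost.** Section 14.6 prevents this.
- **That safety data go uncollected.** Section 13.3 requires every adverse event during enrollment to be documented, and unscheduled visits are summarized separately.
- **That a completer-only table must look too favourable.** The table above shows it can err either way. Lenses are inserted at step 2.8 of Visit 2, before the dispensing criteria at step 2.18, so the Safety Population may include children with only minutes of wear, which can dilute its rate.

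**Conclusion.** The point holds as a defect in how the safety tables are specified, and it should be fixed. As written, the 14.1 rule is too broad, conflicts with items in 14.7, and leaves the defined Safety Population unused. Read literally, it makes the 14.7 counts too low whenever affected children leave before Visit 6, and it biases rates in an unknown direction. Read softly, it leaves the denominators of 14.6 and 14.7 open.

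The size cannot be derived, because the documents give neither event rates nor the number exposed. The share of exposed children omitted lies between near 0 and about 33%, and the upper end is inflated by screen failures. The rates in the illustration rest on assumed event rates and exposure, and on treating completers as the per-protocol set.

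**What to change.** Change section 14 as follows:

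- **14.1:** limit the per-protocol sentence to the efficacy analyses.
- **14.6 and the adverse event items of 14.7:** use the Safety Population by lens. Take children administered any test article as the denominator for subject-level percentages, and count events whenever they were found, including at unscheduled visits.
- **Slit lamp and symptom items of 14.7:** also use the Safety Population by lens. Keep per-visit tables on scheduled visits, with the number of subjects or eyes examined as denominator, and show unscheduled-visit findings separately, as 14.1 already provides.
- **Disposition:** report for all enrolled children, by lens once randomized, so that those who leave before the Visit 2 randomization are shown.
- **Protocol deviations:** report for all randomized children.

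The cost is a few sentences, with no new data. Reported adverse event rates may change in either direction, and per-visit denominators will fall over time as children leave.

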#### 14.2. Sample Size Justification

This is a pilot study for assessing the investigational test articles. As such, the sample size was not determined based on any power analysis with regard to the primary endpoint. The collected data will be used to design future trials. Below sample size calculation is for reference only.

Using the POWER procedure in SAS 9.4, below is the summary of different statistical powers based on the different assumptions of the true difference in each of the primary endpoint at the given sample size (40 per arm). The estimated standard deviation is from the change at 6 months for the test group of the historical study The power analysis was conducted controlling 2-sided type I error of 0.05.

Assuming the true difference in change of axial length (AL) from baseline at 6 months is between 0.05mm to 0.12mm, the table below demonstrates the table below demonstrates the power analysis for the given sample size (40 per arm).

	Estimated Standard		
Difference (Test-Control)	Deviation	# of subjects per arm	Power
0.05	0.10	40	0.60
0.08	0.10	40	0.94
0.10	0.10	40	0.99
0.12	0.10	40	0.99

Assuming the true difference in change of spherical equivalent of cycloplegic auto refraction (SECAR) from baseline at 6 months (in magnitude) is between 0.10D to 0.25D, the table below demonstrates the power analysis for the given sample size (40 per arm).

	Estimated Standard		
Difference (Test-Control)	Deviation	# of subjects per arm	Power
0.10	0.32	40	0.03
0.15	0.32	40	0.54
0.20	0.32	40	0.79
0.25	0.32	40	0.93

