#### 2.3. Hypotheses

#### Primary Hypotheses:

After approximately 6 months of lens wear, at least one of the three Test lenses (EMO-114, -116, and -118) will be efficacious in slowing the progression of myopia compared to the Control lens (EMO-117) such that:

- 1. the change of axial length (AL) of the eye from baseline will be statistically significantly less for the Test lens compared with the Control lens.
- 2. the change of Spherical Equivalent of Cycloplegic Auto Refraction (SECAR) of the eye from baseline will be statistically significantly less in magnitude with the Test lens compared with the Control lens.

Both conditions regarding the performance of the Test lens must be met in order to meet the primary objective.

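### Section 14.2 prints a power of 0.03 for a 0.10 D SECAR difference; its own inputs give 0.28, and a two-sided 5% test cannot have power below 0.05

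*Combined protocol and SAP*

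**What the plan says.** Section 14.2 calls the study a pilot whose size was not derived from a power analysis, and adds: "Below sample size calculation is for reference only". It then gives two tables, one for each co-primary endpoint. The method is introduced as "Using the POWER procedure in SAS 9.4, below is the summary of different statistical powers", and the error rate is fixed: "The power analysis was conducted controlling 2-sided type I error of 0.05". Both tables use 40 subjects per arm. The standard deviations are 0.10 mm for change in axial length (AL) and 0.32 D for change in SECAR, and their source is described: "The estimated standard deviation is from the change at 6 months for the test group of the historical study".

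The SECAR table covers a true difference that "from baseline at 6 months (in magnitude) is between 0.10D to 0.25D". Its first row, in the order difference, SD, subjects per arm and power, reads "0.10 0.32 40 0.03". The next three rows give powers of 0.54, 0.79 and 0.93 for 0.15, 0.20 and 0.25 D.

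The primary hypotheses in section 2.3 require a test lens to succeed on AL and SECAR together: "Both conditions regarding the performance of the Test lens must be met in order to meet the primary objective".

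**The concern.** Within the SECAR table, power jumps from 0.03 to 0.54 when the difference rises by only 0.05 D, while the next two steps of 0.05 D add 0.25 and 0.14. A smooth power curve at a fixed sample size does not do this. The value 0.03 also lies below the nominal error rate of 0.05, so it cannot be the power of the test described.

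The table exists to show what 40 per arm can detect. At the smallest SECAR effect it lists, it gives a reader the wrong answer, and section 14.2 says that the data from this study will be used to design future trials. Because one lens must succeed on both endpoints, its chance of success cannot exceed the lower of its two powers. SECAR is the weaker endpoint over the ranges shown, and the faulty cell is its weakest row.

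**Working it through.** **Inputs, all from section 14.2 except the allocation ratio**

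- Two-sided type I error 0.05.
- n = 40 per arm; allocation is 1:1:1:1 (section 5.1), so each test-versus-control comparison is 40 against 40.
- SD 0.32 D for SECAR and 0.10 mm for AL.
- Differences of 0.10, 0.15, 0.20 and 0.25 D, and of 0.05, 0.08, 0.10 and 0.12 mm.

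The section names the SAS procedure but not the test. I assume a two-sample t-test, and the other rows test that assumption.

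**Formula**

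- Degrees of freedom: 2 × 40 − 2 = 78, so the critical value is t(0.975; 78) = 1.991.
- Noncentrality: λ = difference / (SD × √(2/40)).
- Power = P(T > 1.991) + P(T < −1.991), where T is noncentral t with 78 df and noncentrality λ.

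The standard error is 0.32 × √(2/40) = 0.07155 D for SECAR and 0.10 × √(2/40) = 0.02236 mm for AL.

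**Reproducing the plan's rows**

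| Endpoint | Difference | λ | Computed power | Printed |
|---|---|---|---|---|
| AL | 0.05 mm | 2.236 | 0.598 | 0.60 |
| AL | 0.08 mm | 3.578 | 0.942 | 0.94 |
| AL | 0.10 mm | 4.472 | 0.993 | 0.99 |
| AL | 0.12 mm | 5.367 | 0.9996 | 0.99 |
| SECAR | 0.15 D | 2.096 | 0.544 | 0.54 |
| SECAR | 0.20 D | 2.795 | 0.788 | 0.79 |
| SECAR | 0.25 D | 3.494 | 0.932 | 0.93 |

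Six of these seven rows agree to the printed two decimals. The AL row at 0.12 mm would round to 1.00; the discrepancy is about 0.01 and has no practical meaning. The assumed test and inputs are therefore those behind the tables.

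**The disputed row**

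λ = 0.10 / 0.07155 = 1.398. The upper tail is 0.2811 and the lower tail 0.0004, so power = 0.2815. The normal approximation gives 0.287. The plan prints 0.03. The understatement is 0.28 − 0.03 = 0.25.

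**The floor**

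At a true difference of zero, λ = 0 and power equals the error rate, 0.050. It rises as the difference moves away from zero in either direction. No difference, SD or sample size can give 0.03 at a two-sided 0.05.

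**Could other settings explain 0.03 at 0.10 D?**

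| Variant | Power |
|---|---|
| One-sided 0.05 | 0.398 |
| One-sided 0.025 | 0.281 |
| Two-sided 0.025 | 0.193 |
| Two-sided 0.05/3 | 0.154 |
| Two-sided 0.05/6 | 0.102 |
| Two-sided 0.05, n = 20 per arm | 0.161 |
| Rejection in the wrong direction only | 0.0004 |

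None does. A two-sided error rate of about 0.0012 would be needed, and at that rate the other SECAR rows would be about 0.11, 0.30 and 0.55, not the printed 0.54, 0.79 and 0.93.

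**Effect on joint success**

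Suppose, as an illustration only, that a lens had true effects of 0.05 mm and 0.10 D; the plan does not pair rows across its tables. The ceiling on its chance of meeting both conditions is the smaller of the two powers. From the printed tables that is min(0.60, 0.03) = 0.03; computed, it is min(0.598, 0.2815) = 0.28.

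**The case against.** The strongest reply is that nothing rests on the cell. The plan says its size was not set by power; the targets of 240 enrolled and 160 completing, the analysis model and the decision rule make no use of it; and the error understates power, so it does not oversell the trial. All of that stands and keeps the point minor. It does not make the figure right.

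A second reply is that the digit may have been corrupted when the PDF was read. This cannot be excluded from the text alone. The row is otherwise intact, however, with four well-formed values in order, and 28 is not readily misread as 03. The sensible response is to look at the source table first.

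A third reply concerns the floor. Section 14.5 claims superiority in the beneficial direction only, and the chance of such a claim at zero difference is 0.025, so 0.03 is not below that floor. This is correct for the decision rule, but section 14.2 describes two-sided power, whose minimum is 0.05. Counting only the beneficial direction at 0.10 D still gives 0.281.

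Finally, the pairing of 0.05 mm with 0.10 D is not the plan's. It only illustrates how the cell would be read, and the correction does not depend on it.

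**Conclusion.** The printed 0.03 is wrong. With the section's own inputs the power at 0.10 D is 0.28, so one of eight rows is understated by about 25 percentage points. The 0.28 assumes a two-sample t-test, which the neighbouring rows support. That 0.03 is impossible follows from the stated two-sided 5% error rate alone. The likeliest cause is a slip in typing or transcription, since the remaining rows rule out a different method. Severity is minor: sample size, conduct and analysis are unaffected. The corrected figure is still low, so the table would continue to show that 40 per arm is weak for a SECAR difference of 0.10 D.

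**What to change.** Check the first SECAR row against the original power output, then replace 0.03 with 0.28. If the original already shows 0.28, no change is needed.

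Optionally, add one sentence to section 14.2: the tables give power for each endpoint separately, and because both must be met in the same lens, a lens's chance of success cannot exceed the lower of its two powers.

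The cost is one cell and, if wanted, one sentence.

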#### 14.3. Analysis Populations

#### **Safety Population:**

All subjects who are administered any test article excluding subjects who drop out prior to administering any test article. At least one observation should be recorded.

#### **Per-Protocol Population:**

All subjects who have successfully completed the initial screening and baseline visit (Visit 1), the study lens fitting and dispensing visit (Visit 2), and the 6-month follow up visit (Visit 6), and did not substantially deviate from the protocol as determined by the trial cohort review committee prior to database hard lock (Per-Protocol Population). Justification of excluding subjects with protocol deviations in the per-protocol population set will be documented in a memo to file.

#### Intent-to-Treat (ITT) Population:

All randomized subjects regardless of actual treatment and subsequent withdrawal from study or deviation from protocol. At least one observation should be recorded.

#### 14.4. Level of Statistical Significance

All planned analysis for this study will be conducted with an overall type I error rate of 5%.

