#### 4.2. Study Design Rationale

The study is designed as a study for proof of concept that soft contact lenses with novel optical designs have the potential for controlling myopia progression. A total of three investigational soft contact lenses will be evaluated for their safety and effectiveness of controlling myopia progression in children of 7 to 12 years of age by comparing to an FDA-cleared, non-marketed control contact lens.

Among the three Test lenses, two are of novel optical designs for myopia control (EMO-114 and EMO-118). The third Test lens (EMO-116) with an optical design simulating the MiSight lens (CE-marked for the myopia control indication, not marketed in the US, Canada or China) is included in the study to serve as a reference (positive control) for evaluating the myopia control efficacy of the two novel lens design prototypes (EMO-114 and EMO-118).

The Control lens (EMO-117) used in this study is an FDA-cleared, non-marketed soft contact lens with conventional, single-vision spherical optical design. This lens is selected as the

placebo control for evaluating the optical impact of the three Test lenses on myopia progression.

All four types of test articles are identical in all aspects (lens material, diameter, base curve, modality, and manufacturing process) except for different optical designs.

Since evaluating myopia progression of a subject and the lens effect of controlling myopia progression is longitudinal in nature, a bilateral dispensing, parallel-group study design is required. The designs of the four test articles allow the study to be conducted as a randomized, placebo-controlled, double-masked trial, which is considered to be the gold-standard for a clinical trial. Such clinical trial design and the selection of a soft contact lens as the control are recommended by the expert panel during the FDA workshop to inform the premarket evaluation of contact lenses designed to control myopia progression ([name], September 30, 2016).

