#### 14.5. Primary Analysis

The two primary endpoints, changes of axial length (AL) and cycloplegic auto refraction (SECAR) from baseline at 6 months follow-up, will be analyzed separately using a linear mixed model for longitudinal data. Each model will include treatment group, time period (in weeks) and treatment group by time interaction as fixed effect factors; and site, subject nested in site, and eye nested in subject as random effect factors when appropriate. Other baseline characteristics known of importance such as age, gender, refractive error at baseline, axial length at baseline, pupil size, parental history of myopia and other factors will be included as fixed covariates when appropriate. The covariance between residual errors from the same subject/eye across lens wearing time periods will be selected based on the finite-sample corrected Akaike's Information Criterion. Covariance structures considered may include: Homogeneous Compound Symmetry (CS), first-order autoregressive (AR(1)) and Unstructured covariance structure (UN). For AR (1) structure, site, subject nested in site and eye nested in subject will be included in each model as random effects. For the remaining structures, only site and subject will be included as random effects. The covariance structure that returns the lowest Akaike Information Criteria Corrected (AICC) will be selected as the structure that best fit the data. Heterogeneous residuals covariance structures (R-side) across treatment groups will be considered when appropriate. The log-likelihood ratio test will be

used to test for the homogeneity between the residual covariance structures. The Kenward and Roger method will be used for the denominator degree of freedom.

The null and alternative hypotheses for superiority for each test lens relative to the control are as follows for AL and SECAR:

$$H_0: \Delta_{AL} \ge 0; H_A: \Delta_{AL} < 0;$$
$$H_0: \Delta_{SECAR} \ge 0; H_A: \Delta_{SECAR} < 0,$$

where  $\Delta_{AL}$  and  $\Delta_{SECAR}$  are the mean differences (Test minus Control) in change from baseline of AL and SECAR at 6 months follow-up respectively.

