For each primary endpoint, the comparison between the treatment groups at 6-Month time period will be conducted using a t-test on least-square means from the final model. The corresponding CI of least-square mean (LSM) difference (i.e. LSM change from baseline of test group minus LSM change from baseline for control group) will be calculated with 95% confidence to test the primary hypothesis.

Superiority of the test lens relative to the control lens in reducing change from baseline in axial length at 6-Month will be claimed if the corresponding upper confidence limits of the LSM differences is smaller than 0.

Superiority of the test lens relative to the control lens in reducing the magnitude of change from baseline in cycloplegic auto refraction at 6-Month will be claimed if the corresponding lower confidence limits of the LSM differences is greater than 0.

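### Section 14.4 promises an overall 5% type I error, but success on any one of three lenses with unadjusted 95% intervals can carry a false-claim risk of about 6.2–6.9%

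*Combined protocol and SAP*

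**What the plan says.** Section 14.4 is a single sentence: "All planned analysis for this study will be conducted with an overall type I error rate of 5" per cent. It does not say whether the rate is one- or two-sided.

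Section 2.3 sets the success rule. The primary hypothesis is that "at least one of the three Test lenses (EMO-114, -116, and -118) will be efficacious in slowing the progression of myopia" relative to EMO-117, judged on AL and on SECAR. It adds: "Both conditions regarding the performance of the Test lens must be met in order to meet the primary objective".

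Section 14.5 applies this lens by lens: "The null and alternative hypotheses for superiority for each test lens relative to the control are as follows for AL and SECAR". Those hypotheses are one-sided. The interval for each difference from control "will be calculated with 95% confidence to test the primary hypothesis", and superiority is claimed when the limit on the relevant side excludes zero.

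Section 14.2 says of its power tables: "The power analysis was conducted controlling 2-sided type I error of 0.05".

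Sections 14.4 to 14.10 give no adjustment, testing order or gatekeeping across the three lenses. The only gate, in section 14.7, governs later comparisons among the test lenses.

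On the status of the trial, section 14.2 says: "This is a pilot study for assessing the investigational test articles". Section 4.2 says: "The study is designed as a study for proof of concept".

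**The concern.** The decision rule has two layers. Within a lens, AL **and** SECAR must both succeed. This cannot raise the error above the level of a single test. Across lenses, EMO-114 **or** EMO-116 **or** EMO-118 may succeed, which gives three chances of a false claim. An overall rate has to hold for every pattern of true effects, including lenses that move one endpoint and not the other. Nothing in the plan limits the rate to 5% in those patterns.

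The missing sidedness matters because the size of any adjustment depends on it: section 14.2 works two-sided, while the hypotheses in section 14.5 are one-sided.

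At stake is the accuracy of the report. A statement that the primary objective was met at an overall 5% would credit the analysis with a property it does not have. The primary result also opens the further comparisons in section 14.7, and section 14.2 says the data will feed the design of later trials.

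**Working it through.** **Inputs.** Three test lenses and one control, 1:1:1:1 (section 5.1); 40 per arm, SD 0.10 mm for AL and 0.32 D for SECAR (section 14.2); 95% intervals, read as two-sided (section 14.5). Assumed: residual df 4 × 39 = 156, and AL/SECAR correlation ρ from 0 to 0.9, because the documents give none. Effects are signed so that positive favours the test lens. The SECAR hypotheses and the SECAR claim rule in section 14.5 point in opposite directions. That needs reconciling separately and does not alter the error rate.

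**1. The plan's own power figures.** A two-group noncentral t calculation (df 78, two-sided 0.05, 40 per arm) gives 0.942 for AL 0.08 mm (stated 0.94) and 0.788 for SECAR 0.20 D (stated 0.79). Seven of the eight rows reproduce. The SECAR 0.10 D row (stated 0.03, computed 0.28) does not, which is a separate error. So planning used 5% per comparison, with no allowance for three lenses.

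**2. One lens.** A two-sided 95% interval leaves 2.5% in the favourable direction (critical t 1.975). With both endpoints required, a lens's error approaches 2.5% when it is null on one endpoint and has a large effect on the other.

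**3. Upper bound for three lenses.** 3 × 0.025 = 0.075.

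**4. All three lenses null on the same endpoint, large effect on the other.** Each contrast has variance 2σ²/n and any two share the control term σ²/n, so their correlation is 0.5. The error is 1 − P(all three Z < 1.96) = 0.0627, or 0.0625 with the t distribution. Simulation gives 0.0623–0.0627 over ρ.

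**5. Mixed null: two lenses null on AL, the third null on SECAR.** Contrasts on different endpoints have correlation 0.5ρ. Simulated results (2 million draws per case):

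| True effect on the non-null endpoint | ρ = 0 | 0.5 | 0.7 | 0.9 |
|---|---|---|---|---|
| Large | 0.0690 | 0.0667 | 0.0657 | 0.0637 |
| 0.10 mm / 0.25 D | 0.0660 | 0.0670 | 0.0656 | 0.0636 |
| 0.08 mm / 0.20 D | 0.0589 | 0.0664 | 0.0650 | 0.0633 |

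The trivariate normal calculation for large effects gives 0.0692, 0.0670, 0.0656 and 0.0638.

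**6. No lens affects either endpoint.** 0.0019, 0.0126, 0.0220 and 0.0383 at ρ = 0, 0.5, 0.7 and 0.9. Here 5% holds.

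**7. Candidate corrections, with a lens's p-value taken as the larger of its two endpoint p-values.**

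- Bonferroni, one-sided 5%: t at 1 − 0.05/3 is 2.147; mixed-null rate about 0.047 at ρ = 0.
- Bonferroni, two-sided 5%: t at 1 − 0.025/3 is 2.420; about 0.024 in the favourable direction.
- Holm: at most 0.0491 and 0.0247 in the cases simulated.
- Per-endpoint Dunnett values (2.078 and 2.372): 0.0509–0.0548 and 0.0254–0.0269 under the mixed null. These are not enough, because they protect only when the same endpoint is null for every lens.

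**The case against.** Four points deserve weight.

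- **EMO-116 is the positive control** (sections 1.1 and 4.2). If it truly works on both endpoints, only two lenses can be claimed falsely and the rate is at most 2 × 2.5% = 5.0%. It is about 4.5% when both novel lenses are null on the same endpoint, and at most 1 − 0.975² = 4.9% when they are null on different ones. This is correct, but section 2.3 counts EMO-116 among the three lenses whose success is being tested, so the rule cannot presuppose its efficacy.
- **The excess needs a particular state of nature**: lenses that move one endpoint and not the other. The documents do not say how likely that is.
- **Small effects weaken it.** At the bottom of the section 14.2 ranges (0.05 mm and 0.10 D), the mixed-null rate runs from 2.8% at ρ = 0 to 6.4% at ρ = 0.9, so whether 5% is passed there depends on the unknown correlation.
- **It is a pilot.** Whether to adjust across separate arms in a proof-of-concept study is a matter of judgement, and adjusting costs power.

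All four limit the practical importance and favour a light remedy. None makes the sentence in section 14.4 true: the plan sets formal hypotheses and claim criteria, and an overall rate is a statement about the worst case. The calculation also uses a simple t-test rather than the two-eye mixed model of section 14.5, so the third decimal should not be pressed. The bound and the general size do not depend on that.

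**Conclusion.** The concern holds. As written, section 14.4 claims control that the rule in sections 2.3 and 14.5 does not deliver. The worst-case chance of a false lens claim is about 6.2–6.9%, an excess of 1.2–1.9 percentage points if the 5% is one-sided. If it is two-sided, the favourable-direction target is 2.5% and the shortfall is relatively larger, so the promise fails on either reading. The figures rest on 40 per arm, a shared control, two-sided 95% intervals and an assumed endpoint correlation of 0 to 0.9. The effect is modest and bounded, but the contradiction should be fixed because the repair is nearly free.

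**What to change.** Choose one.

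**(a) Restate section 14.4.** For example: *the type I error rate is 5% two-sided for each comparison of a test lens with EMO-117; a lens must succeed on both AL and SECAR; no adjustment is made across the three lenses.* This costs one sentence and no power, and it suits a pilot. The report should then not describe the result as controlled at an overall 5%.

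**(b) Keep the overall 5%.** State its sidedness in section 14.4, and add to section 14.5 a Bonferroni or Holm step across the three lenses, using the larger of each lens's AL and SECAR p-values. No new data are needed, but power at 40 per arm falls under Bonferroni:

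| | Unadjusted | One-sided 5% | Two-sided 5% |
|---|---|---|---|
| AL 0.08 mm | 0.945 | 0.923 | 0.875 |
| SECAR 0.20 D | 0.793 | 0.741 | 0.646 |
| Both endpoints, ρ 0 to 0.9 | 0.75–0.79 | 0.68–0.74 | 0.57–0.64 |

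Holm loses no more than Bonferroni.
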